### **6.6.1.5. Time to discontinuation from IP due to Gastrointestinal Disorders AEs**

Exploratory summaries on the time to discontinuation from IP (regardless of study discontinuation or continuation) due to Gastrointestinal Disorders AEs (defined as based on System Organ Class) will be produced with a Cumulative Incidence Plot as described in Section 5.2.7. Participants who discontinue will be censored at the associated discontinuation date.

## **6.6.2. Laboratory Data**

Laboratory data from will be listed and summarized by treatment and overall, in accordance with the sponsor reporting standards. Baseline is as defined in Section 3.5.3.

### 6.6.2.1. Focused Laboratory Summaries on Endpoints of Interest

Absolute values, changes from baseline and percent changes from baseline in calcitonin, amylase, lipase, TSH, free T4, lipid profile, liver function tests and eGFR (as outlined in Section 3.5.3.1) will be summarized by treatment and time point as per Section 5.2.1 (unplanned readings will not be included in these summaries). Follow-up data will be included in the summaries with data from all participants in the safety analysis set. Tables will be paged by parameter. Baseline is as defined in Section 3.5.3.

The following box and whisker plots for each parameter will be produced:

- Absolute values over time by treatment
- Change from baseline over time by treatment
- Percentage change from baseline over time by treatment

MMRM models (as described in Section 5.2.3) will be applied to the change from baseline at Weeks 2 (only for liver function tests and eGFR), 4, 6 (only for liver function tests and eGFR), 8, 12 and 16 for each parameter separately using the safety analysis set (as defined in Section 4). From each model, the LSMeans together with 90% confidence intervals, standard errors and 2-sided p-values will be obtained for each treatment at each time point. Differences in LSMeans between each dose of PF-06882961 relative to placebo at each time point, together with 90% confidence intervals, standard errors and 2-sided p-values will also be obtained. A plot of the LSMean differences to Placebo (including 90% confidence intervals) over time, with a separate line for each dose of PF-06882961 will be produced separately for each parameter. Standard SAS outputs will be provided to support the main statistical summary tables but will not be included in the CSR.

Additionally, MMRM models will be applied to the changes from baseline in Triglycerides, ALT, AST, Alkaline Phosphatase and GGT for each parameter separately on the natural log scale at the same above relevant weeks using the safety analysis set. This parameter list may be expanded after review of unblinded tables if MMRM diagnostics reveal any other residuals that deviate substantially from a normal distribution and require log transformation for interpretation. In the models, the related baseline will be included on the natural log scale also. Similar outputs will be reported as above, where the percent change from baseline or percent difference to placebo (as applicable) will be reported as calculated using:

$$\text{Percent change} = 100 * (\text{back-transformed LSMean} - 1)$$

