## 4.2. Scientific Rationale for Study Design

This study is designed to assess the efficacy of PF-06882961 on glycemic control, measured by HbA1c, in participants with T2DM over 16 weeks of dosing. A placebo run-in period (ie, V2 to V3) is included in this study to familiarize participants with the study treatment regimens and to exclude those who are not compliant with blinded placebo dosing prior to randomization. Clinical laboratory tests, assessments of vital signs and 12-lead ECGs, physical examinations, and AE monitoring will provide data to evaluate the efficacy, safety and tolerability of PF-06882961.

As part of the clinical safety laboratory tests, calcitonin, amylase, and lipase will be assessed, as these laboratory parameters have been shown to increase with marketed GLP-1R agonists. In addition, thyroid stimulating hormone (TSH), free thyroxine (FT4), lipids, coagulation profile and total bile acids (TBA) will be assessed, based on non-adverse findings in the nonclinical studies with PF-06882961.

The total duration of dosing in this study will be 16 weeks for all participants. Based on the tolerability data to date from C3421002, the lower doses of 2.5 and 10 mg BID are expected to be well-tolerated without the need for titration, and thus will be dosed at the same dose level for all 16 weeks of the study. The intermediate doses of 40 and 80 mg BID will involve titration and reach the target dose level within 3 to 5 weeks of initiating dosing, respectively. For the highest dose level of 120 mg BID, the target dose level will be reached in the seventh week of dosing. Downward titration or dosing is not permitted during the study; participants who do not tolerate the titration scheme and/or assigned dose may be required to discontinue dosing of IP. Titration schemes are provided in [Section 6.1](#), and additional details regarding titration are provided in the IP Manual.

An interim analysis may be performed to assess safety, and a dose level may be dropped if deemed necessary. See [Section 4.4](#) and [Section 9.5](#) for additional information regarding Interim Analyses.

All doses will be blinded and consist of 4 tablets administered BID via a blister pack, and dosing regimens will look the same between the placebo run-in and the 16-week dosing duration post randomization.

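### Which further laboratory parameters get an added log-scale model is decided after unblinded tables are seen, with no threshold, though blinded data could settle it

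*SAP*

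**What the plan says.** SAP 6.6.2.1 (Focused Laboratory Summaries on Endpoints of Interest) covers this set: "Absolute values, changes from baseline and percent changes from baseline in calcitonin, amylase, lipase, TSH, free T4, lipid profile, liver function tests and eGFR". Each parameter gets descriptive tables, box plots and an MMRM of change from baseline on the original scale. The reporting for these models is: "From each model, the LSMeans together with 90% confidence intervals, standard errors and 2-sided p-values will be obtained for each treatment at each time point". The same applies to differences from placebo.

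A second set of models follows: "Additionally, MMRM models will be applied to the changes from baseline in Triglycerides, ALT, AST, Alkaline Phosphatase and GGT for each parameter separately", this time on the natural log scale. The list can then grow: "This parameter list may be expanded after review of unblinded tables if MMRM diagnostics reveal any other residuals that deviate substantially". The sentence completes the condition with "deviate substantially from a normal distribution and require log transformation for interpretation". No skewness value, test or other cut-off is given, and the verb is permissive.

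Protocol 4.2 explains why three of the tests off the log list are measured: "calcitonin, amylase, and lipase will be assessed, as these laboratory parameters have been shown to increase with marketed GLP-1R agonists".

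Two other places bear on the point. SAP 5.2.3 has a general diagnostics clause for every MMRM. It lists outliers beyond 3 studentized residuals, allows transformations to be investigated, and asks for justification in the report. It sets no timing. SAP Section 1 (Version History) gives blinded data reviews as one reason for version 2.

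**The concern.** An analysis added after arm-level results are known is hard to defend, even when the reason for adding it is sound. A reader of the report cannot tell whether a log-scale lipase model is there because the residuals were poor or because the raw-scale result invited a second look. Nor can the reader tell whether its absence for another test means acceptable residuals or no interest in looking. Without a threshold, adding a parameter and leaving it out both comply with the SAP.

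The tests left open include the three that the protocol ties to the drug class, and the study is meant to support dose selection. At stake is the credibility of the modelled comparisons for those tests and which of two scales is emphasised in the report. No efficacy conclusion is at stake.

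**Working it through.** No figure in the documents bears on this point, so the check is a count, a comparison of the texts, and an illustration on stated assumptions.

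**1. How many parameters are open.** SAP 3.5.3.1 expands the groups: calcitonin, amylase, lipase, TSH and free T4 (5), lipid profile (4), liver function tests (6) and eGFR (1). The total is 5 + 4 + 6 + 1 = 16. Five are named for the log scale: triglycerides, ALT, AST, alkaline phosphatase and GGT. That leaves 16 - 5 = 11: calcitonin, amylase, lipase, TSH, free T4, total cholesterol, LDL, HDL, total bilirubin, bile acids and eGFR.

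**2. What one addition brings.** SAP 6.6.2.1 models lipase, amylase, calcitonin and TSH at Weeks 4, 8, 12 and 16. One added model therefore gives 5 doses x 4 visits = 20 comparisons with placebo. With no true effect, 20 x 0.10 = 2 of the 90% intervals would be expected to exclude zero.

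**3. Does the decision need unblinding?** The planned MMRM includes treatment, so its exact residuals need the codes. Marked skewness also shows in residuals from a pooled model without treatment, and blinded reviews were already part of this study's process.

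**4. Illustration of the cost of choosing by result.** The documents give no distributions, so all inputs here are assumptions: log-normal values, log-scale SD 0.3, 0.5 or 0.8, baseline correlation 0.6 on the log scale, no true effect, 50 per arm, one dose against placebo by ANCOVA, 2-sided 10% level, 4,000 runs per setting. The blinded rule uses the log scale if pooled residual skewness exceeds 1.

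| Log-SD | Raw scale only | Log scale only | More favourable scale | Blinded rule |
|---|---|---|---|---|
| 0.3 | 9.8% | 9.6% | 11.6% | 9.8% |
| 0.5 | 10.4% | 10.0% | 13.3% | 9.9% |
| 0.8 | 10.3% | 10.6% | 15.2% | 10.6% |

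The simulation standard error is sqrt(0.1 x 0.9 / 4000) = 0.5 points. Either scale fixed in advance holds its level, and so does the blinded rule. Only selection by result inflates it.

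**5. Illustration of power.** Further assumptions: 55 per arm, true rise 15-30%, log-SD 0.35-0.6 between and 0.25-0.5 within participants. Power was 51-69% on the raw scale and 67-73% on the log scale. The gain was 4-15 points with log-normal noise and 8-20 points with heavier-tailed t(4) noise. These figures show why a log-scale model can be worth having for a skewed test. They do not measure bias from choosing after unblinding.

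**The case against.** The best defence is that nothing is replaced. A reader might infer that the scale for lipase or amylase is picked with the arm results in view. The SAP does not support that. The raw-scale model is fitted and reported for every parameter, the log-scale model is additional, five parameters are fixed in advance, and the stated trigger is residual diagnostics. This defence stands, and it narrows the point to the choice of an extra analysis and the emphasis given to it.

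Other points on that side also carry weight:

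- Residuals of the planned model exist only after unblinding. That is true, but a pooled screen is adequate for deciding whether a log model is sensible.
- SAP 5.2.3 requires justification for alternatives. That helps transparency, but it is also optional in application and sets neither timing nor threshold.
- Percent-change tables and box plots cover all 16 parameters. The flag and alert counts in SAP 3.5.3.2 and 6.6.2.2 cover amylase, lipase, calcitonin, bilirubin and bile acids whatever the modelling scale. These are safeguards, though descriptive ones. Without an addition, the raw-scale model remains the only modelled comparison.
- The laboratory endpoints have no estimands (Protocol Section 3), the protocol plans descriptive safety summaries (9.4.2), the hypotheses in SAP 5.1 concern efficacy only, and SAP 6.6.1 calls safety analysis generally exploratory. This limits the consequence and is accepted.

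**Conclusion.** The point holds as an avoidable unblinded choice of an additional analysis for up to 11 of 16 focused laboratory parameters, on a criterion without a threshold. It is a stated timing rule in the SAP, not a missing detail. Its consequence is modest: possible selective emphasis in exploratory safety models. The primary and secondary efficacy analyses are unaffected.

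The illustrated 11.6-15.2% false-positive rate is an upper bound under assumed log-normal data. It requires that only the favourable scale be reported, which the SAP does not plan. A reader might also infer that the plan loses a known amount of power by leaving these tests on the raw scale. The documents do not support a figure: they give no distributions for these tests, and no decision rule depends on a laboratory p-value.

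**What to change.** In SAP 6.6.2.1, delete the words that place the expansion after review of unblinded tables, and close the log-scale list before unblinding by one of two routes:

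- name the extra parameters now: amylase, lipase, total bile acids, TSH and total bilirubin, plus calcitonin unless many results are below quantification; or
- state a residual criterion and apply it to pooled blinded residuals, from a model without treatment, at the blinded data review.

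Keep the raw-scale models for all parameters. State that any parameter added later, including under the transformation clause in SAP 5.2.3, is reported on both scales and labelled post hoc. That last sentence is needed because SAP 5.2.3 would otherwise leave the same choice open.

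The cost is SAP wording, five or six extra model runs under the first route, and the outputs that go with them.

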### 6.6.2.2. Clinical Laboratory Parameters of Interest

An additional summary table of the number of participants (from the Safety Analysis Set as defined in Section 4) with “Flag Level” or “Alert Level” abnormalities for each of the clinical laboratory parameters of interest as specified in Section 3.5.3.2 will be produced.

This table will summarise the number of participants with “Flag level” or “Alert level” abnormalities separately and by treatment group and placebo run-in and overall (i.e. post-dose), as per Section 5.2.2.

### 6.6.3. Vital Signs

Average of the triplicate measurements (where applicable) will be used in analyses.

Absolute values and changes from baseline in supine systolic and diastolic blood pressure and pulse rate will be summarized by treatment and time point, according to sponsor reporting standards. Tables will be paged by parameter. Baseline is as defined in Section 3.5.3.2.

Mean changes from baseline for systolic and diastolic blood pressure and pulse rate will be plotted against time point. On each plot there will be 1 line for each treatment with all treatments on the same plot including placebo.

MMRM models (as described in Section 5.2.3) will be applied to the change from baseline at Weeks 2, 4 (0 and 2H separately), 6, 8 (0 and 2H separately), 12 and 16 (0 and 2H separately) for supine systolic and diastolic blood pressure and pulse rate separately using the safety analysis set (as defined in Section 4). From each model, the LSMMeans together with 90% confidence intervals, standard errors and 2-sided p-values will be obtained for each treatment at each time point. Differences in LSMMeans between each dose of PF-06882961 relative to placebo at each time point, together with 90% confidence intervals, standard errors and 2-sided p-values will also be obtained. A plot of the LSMeans differences to Placebo (including 90% confidence intervals) over time, with a separate line for each dose of PF-06882961 will be produced separately for each parameter. Standard SAS outputs will be provided to support the main statistical summary tables but will not be included in the CSR.

Maximum absolute values and maximum changes from baseline for vital signs, over all measurements taken post dose will also be tabulated by treatment using categories as defined in the Appendix 5. Numbers and percentages of participants meeting the categorical criteria will be provided. All planned and unplanned post dose time points will be counted in these categorical summaries. All values meeting the criteria of potential clinical concern will be listed.

Maximum decrease and increase from baseline for supine systolic and diastolic blood pressures, and maximum increase from baseline for supine pulse rate will be summarized by treatment, according to sponsor reporting standards.

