## **7. DISCONTINUATION OF STUDY INTERVENTION AND PARTICIPANT DISCONTINUATION/WITHDRAWAL**

### **7.1. Discontinuation of Study Intervention**

It may be necessary for a participant to permanently discontinue IP. If a safety or tolerability concern arises, in particular if not responsive to symptomatic management, dosing with double-blinded IP may be stopped in an individual participant at investigator discretion.

Per the study estimands, if IP is permanently discontinued, the participant will remain in the study and continue to follow all protocol specified visits and procedures according to the SoA with the exception of dosing activities CCI

The site should notify the Sponsor Medical Monitor or Sponsor Clinician if the below criteria for permanent discontinuation are met.

Note that discontinuation of IP does not represent withdrawal from the study.

See the SoA for data to be collected at the time of intervention discontinuation and follow-up and for any further evaluations that need to be completed.

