### 9.3. Populations for Analysis

For purposes of analysis, the following populations are defined:

Population	Description
Enrolled	All participants who sign the ICD.
Randomly assigned to investigational product	All participants randomly assigned to IP regardless of whether or not IP was administered.
Evaluable	All participants randomly assigned to IP and who take at least 1 dose of IP. Participants will be analyzed according to the randomized intervention.
Safety Analysis Set	All participants randomly assigned to IP and who take at least 1 dose of IP. Participants will be analyzed according to the product they actually received.

Defined Population for Analysis	Description
Estimand Set 1A (related to estimands 1A, 2, 3, and 4)	All participants randomly assigned to IP and who take at least 1 dose of IP. For participants who discontinue IP and/or receive glycemic rescue medication, all subsequent values will be censored.
CCI [REDACTED]	[REDACTED]
[REDACTED]	[REDACTED]
[REDACTED]	[REDACTED]

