### **3.5.1.1. Subset Reporting Interval**

A summary of adverse events occurring during a subset of the main reporting interval will be based on a shorter reporting window. This will include all TEAEs starting after or on the first dose, but doesn't start more than two days after the last dose of IP (defined as either completing the 16 weeks of treatment or discontinuing from IP earlier).

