### **6.6.1.3. Time to First Occurrence/Recurrence of AEs of Interest**

Exploratory summaries on the time to the first occurrence of AEs of interest will be produced in Cumulative Incidence Plots as described in Section 5.2.7. Participants who discontinue from the study, discontinue from IP or initiate glycemic rescue medication prior to the start of the AE event of interest will be censored at the discontinuation/initiation date.

The three AEs of interest are: diarrhoea, nausea and vomiting (based on preferred term). A separate plot for each AE will be produced separately.

The above will also be produced separately for the time to the first recurrence of the three AEs of interest.

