### **6.6.1.4. Percentage of Participants with Ongoing AEs of Interest**

Exploratory summaries on the percentage of participants reporting AEs of interest will be produced by week and treatment and overall as per Section 5.2.2 from Week 1 up to Week 18 (i.e. including the follow-up visit 10).

To calculate the percentage each week, the total number of participants who experience the TEAE of interest at any time during the respective week will be the numerator and the total number of participants who had not discontinued from IP and/or the study prior to that respective week will be the denominator (note if a participant did discontinue from IP and/or the study during that respective week they would be included in the denominator).

A line plot of the percentages over each week will be produced based on the summary statistics with a separate line for each treatment.

The AEs of interest are diarrhoea, nausea and vomiting (based on preferred term); where a separate table and plot will be produced for each AE.

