### 6.6.4. Electrocardiograms

Average of the triplicate measurements (where applicable) will be used in analyses. Absolute values and changes from baseline in QT, heart rate, QTcF, PR and QRS will be summarized

by treatment and time point using sponsor reporting standards. Tables will be paged by parameter. Baseline is as defined in Section 3.5.5.

Mean changes from baseline in QT, heart rate and QTcF will be plotted against time point. On each plot there will be 1 line for each treatment with all treatments included on the same plot including placebo.

MMRM models (as described in Section 5.2.3) will be applied to the change from baseline at Weeks 2, 4 (0 and 2H separately), 6, 8 (0 and 2H separately), 12 and 16 (0 and 2H separately) for QT, heart rate and QTcF separately using the safety analysis set (as defined in Section 4). From each model, the LSMeans together with 90% confidence intervals, standard errors and 2-sided p-values will be obtained for each treatment at each time point. Differences in LSMeans between each dose of PF-06882961 relative to placebo at each time point, together with 90% confidence intervals, standard errors and 2-sided p-values will also be obtained. A plot of the LSMean differences to Placebo (including 90% confidence intervals) over time, with a separate line for each dose of PF-06882961 will be produced separately for each parameter. Standard SAS outputs will be provided to support the main statistical summary tables but will not be included in the CSR.

ECG endpoints and changes from baseline (QTcF, PR and QRS) will also be summarized descriptively by treatment using categories as defined in the Appendix 5 (for QTc these correspond to the Pfizer Guidance (3) as referenced in Section 8). Numbers and percentages of participants meeting the categorical criteria will be provided. All planned and unplanned postdose time points will be counted in these categorical summaries. All values meeting the criteria of potential clinical concern will be listed.

Maximum absolute value (post dose) and the maximum increase from baseline for QTcF, PR and QRS will be summarized by treatment according to sponsor reporting standards.

Listings of participants with any single post dose value > 500 msec will also be produced for QTcF.

CCI

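### The pulse-rate and ECG heart-rate MMRMs show no rule for readings taken after IP is stopped, and no on-treatment companion is visible, so a quickly reversing heart-rate effect may be understated by an unknown amount

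*SAP*

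**What the plan says.** - **Which readings enter the models.** SAP 6.6.3 fits MMRMs "for supine systolic and diastolic blood pressure and pulse rate separately using the safety analysis set (as defined in Section 4". SAP 6.6.4 does so "for QT, heart rate and QTcF separately using the safety analysis set (as defined in Section 4". SAP Section 4 defines the Safety Analysis Set as participants randomized who took at least one dose, analysed as treated. It has no censoring clause.
- **What happens after a stop.** Under Protocol 7.1 a participant who permanently stops IP stays in the study and will "continue to follow all protocol specified visits and procedures according to the SoA with the exception of dosing activities". The end of that sentence is redacted.
- **Efficacy data.** Protocol 9.3 sets the contrasting rule for Estimand Set 1A: "For participants who discontinue IP and/or receive glycemic rescue medication, all subsequent values will be censored". SAP 5.3 refers only to censoring of efficacy data. SAP 5.2.3 mentions values missing through censoring but sets no rule of its own.
- **Adverse events.** SAP 3.5.1.1 and 6.6.1.1 add a subset to the full AE summary, leaving out events that "start more than two days after the last dose of IP". In SAP 6.6.1.3, participants who "discontinue from IP or initiate glycemic rescue medication prior to the start of the AE event of interest will be censored" at the date of the stop or the start of rescue.
- **Status of these endpoints.** Vital signs and ECG parameters are secondary safety endpoints with no defined estimand (Protocol 3).

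**The concern.** Off-drug readings at scheduled weeks are expected by design, and they enter the arm means with the same weight as on-drug readings. If the drug raises heart rate and the effect goes away soon after the last dose, those readings pull the difference from placebo towards zero, which is the reassuring direction for a safety endpoint.

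The study is meant to support dose selection (Protocol 2.1). Protocol 4.2 forbids downward titration and says participants who cannot tolerate their dose may have to stop IP, so the off-drug share may rise with dose. A heart-rate difference that flattens at 80 or 120 mg could then be a true plateau or the effect of more stopping. The planned MMRM alone gives no on-drug mean difference to separate the two. According to the SAP version history, these MMRMs replaced the summaries of differences to placebo for vital signs and ECG.

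**Working it through.** **Plan's own figure.** The plan states none for the safety MMRMs. Its one design calculation, 80% power for HbA1c, reproduces: 0.804 by the normal approximation and 0.799 by the t-test with 50 per arm, and 67 x 0.75 = 50.25 completers. Nothing below depends on it.

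**Formula.** Let D be the on-drug difference from placebo, f the share of attending participants in the active arm who are off IP at the visit, and r the part of the effect left after stopping. Then

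observed difference = D x [1 - f x (1 - r)], so loss = f x (1 - r) x D.

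**Inputs.**
- D: Protocol 2.2.2.1 reports mean heart-rate increases of 5 to 15 bpm. It does not say they are placebo-adjusted, so using them as D is an assumption.
- f: not given. Protocol 2.2.2.1 has 6 of 98 participants leaving a 28-day study, and Protocol 9.2 plans for 25% drop-out. Neither is f, because people who leave give no later readings. I take 0 to 25%. The top holds only if every planned loss is an IP stop and every stopper still attends.
- r: assumed 0 (full reversal).

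**Loss in bpm at r = 0.**

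| f | D = 5 | D = 10 | D = 15 |
|---|---|---|---|
| 0% (stoppers leave the study) | 0 | 0 | 0 |
| 5% | 0.25 | 0.5 | 0.75 |
| 10% | 0.5 | 1.0 | 1.5 |
| 14.3% (25% stop, half attend: 0.125/0.875) | 0.7 | 1.4 | 2.1 |
| 25% (upper bound) | 1.25 | 2.5 | 3.75 |

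If half the effect persists (r = 0.5), f = 25% and D = 10, the observed difference is 8.75 bpm, a loss of 1.25.

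**Set against the noise.** The SE of a difference between two arms of 67 is SD x sqrt(2/67) x sqrt(1 - 0.09), with baseline assumed to explain 9% of the variance. For an assumed SD of 9 bpm this is 1.48; for SD 7 and 11 it is 1.15 and 1.81. At f = 10% or less, the loss is no more than about one SE.

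**Does the MMRM behave as the formula says?** This was simulated with all settings assumed: 67 per arm, the six scheduled visits, SD 9, correlation 0.5, full effect by Week 8, uniform stop times, full reversal, 25% of active and 5% of placebo stopping, true D = 10.

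| Stoppers still attending | Week 16, all readings | Week 16, on-treatment | Week 8, all readings | Week 8, on-treatment |
|---|---|---|---|---|
| None | 9.95 | 9.95 | 9.92 | 9.92 |
| Half | 8.53 | 9.94 | 9.28 | 9.93 |
| All | 7.50 | 10.02 | 8.75 | 10.01 |

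The loss matches f x D, and at Week 8 it is about half that at Week 16.

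**If stopping depends on the unobserved current pulse**, MAR fails. With about 25 to 27% stopping, half or all of the stoppers attending and true D of 5 to 15 bpm, the on-treatment model then lost 0.2 to 0.4 bpm at Week 16, against 0.8 to 4.0 bpm for all readings.

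**The case against.** The strongest reply is that the planned analysis is a legitimate choice. These endpoints have no estimand, SAP 6.6.1 describes safety analysis as generally exploratory, and an all-readings comparison answers a real question. That stands: the model is not an error.

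Several other points also stand and limit the claim.
- **Other outputs help.** SAP 6.5.6 and 6.6.1.5 plot time to stopping IP by arm, differences are reported at every visit, and the maximum-change and category tables are not diluted in this way. A reader might infer that stopping and plateau cannot be told apart at all; that goes too far. What these outputs lack is an on-drug mean difference and a count of off-drug readings at each visit.
- **The 2-hour readings may already be mostly on-drug.** Protocol 7.1 excepts dosing activities, so it is unclear whether stoppers give post-dose readings.
- **Something may be hidden.** Protocol 9.6 plans a partly redacted PD analysis expected to include vitals and ECGs, parts of the SAP are redacted, and sponsor reporting standards are not shown. One can say only that no on-treatment counterpart is visible.
- **The AE precedent is narrower than it looks.** The weekly AE percentages (SAP 6.6.1.4) might be read as a third on-treatment output. There "the total number of participants who had not discontinued from IP and/or the study prior to that respective week will be the denominator", but the numerator has no stated on-IP limit. Only the 2-day subset pairs a full version with a restricted one; the time-to-AE plots censor at the stop but have no all-data twin.

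**Conclusion.** The point holds as a worthwhile, low-cost addition for pulse rate and ECG heart rate. The direction of the bias is clear for an effect that reverses quickly. Its size is not: it could be nil, is about 0.5 to 1.5 bpm at an assumed 10% off IP, and cannot exceed 1.25 to 3.75 bpm within the range considered. These figures assume full reversal and treat the 5 to 15 bpm as a placebo difference.

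Three stronger readings are not supported:
- **That the planned models are invalid or hide a signal.** They give a valid treatment-policy result, and the off-IP share may be small.
- **That blood pressure, QT, QTcF and the focused laboratory tests are equally affected.** The laboratory MMRMs are also fitted "for each parameter separately using the safety analysis set (as defined in Section 4", but the documents give no effect size for any of these measures, and slowly reversing laboratory tests may hardly change.
- **That a 25% dilution is to be expected.** The 25% is a planning drop-out rate, not a rate of attending while off IP.

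The HbA1c analysis is not touched.

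**What to change.** In SAP 6.6.3 (pulse rate) and 6.6.4 (heart rate), keep the planned MMRM and add text to this effect: *The same MMRM will be fitted to readings taken up to 2 days after the last dose of IP, with later readings treated as missing. Both results will be shown side by side, with the number of readings per arm and visit taken after that window, pre-dose and 2H separately.*

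The 2 days is borrowed from the AE subset in SAP 3.5.1.1. The visible documents give no half-life to check it against, so the sponsor should confirm it or replace it. The counts alone would show whether dilution matters, and would settle how many 2H readings had no dose before them. Extension to blood pressure, QT and QTcF is optional; none is asked for the laboratory tests.

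The cost is a few extra model runs and tables, with no new data, visit or protocol change. The added analysis relies on MAR after the stop, as the primary efficacy analysis already does (Protocol 9.1.1). In the simulations precision was similar: SE 1.45 to 1.47 bpm on-treatment, against 1.38 to 1.59 for all readings. No planned result is removed.
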